# 1. INTRODUCTION

# 1.1 Background

Alcohol related conditions account for up to 40% of weekday Emergency Department attendances. II Socioeconomic deprivation has a well-proven association with rates of alcoholism in the community. Glasgow Royal Infirmary serves the north and east of Glasgow, parts of which have been designated by the WHO to be among the most deprived areas in Europe.

Between 30-80% of chronic alcoholics have thiamine deficiency. The incidence of Korsakoff's psychosis has been noted to be steadily increasing in the East End of Glasgow since 1990. Wernicke-Korsakoff Psychosis has also been shown to be related to Thiamine deficiency. Magnesium ( $Mg^{2+}$ ) is known to be an essential cofactor for Thiamine, though its effect on the enzyme transketolase, in the Pentose Phosphate Shunt and as such is advocated by core Emergency Medicine texts in the treatment of alcoholic or malnourished patients.

The aim of this project is to further clarify the effect of concurrent magnesium supplementation with thiamine administration on Red Cell Transketolase (TKA) Activity in a cohort of alcoholic patients admitted through ED. Patients will be determined to be alcohol dependent from history (FAST questionnaire) or in alcohol withdrawal as determined by the GMAWS scale (appendix).

# 1.2 Rationale

#### Thiamine and Magnesium in the Alcohol Withdrawal Patient

Chronic alcoholics have a 30-80% incidence of clinical or biochemical signs of thiamine deficiency. Wernicke's Encephalopathy (WE) is not a rare disorder. Autopsy studies have revealed a prevalence of 2% in western society among the general population. Untreated WE has a mortality rate of 20% and a progression along its clinical spectrum to Korsakoff psychosis of 85%.

Parenteral thiamine replacement is standard practice in the treatment of alcoholic patients presenting to the A&E department. However despite the fact that routine co-supplementation with magnesium sulphate is practiced by many doctor's in the treatment of these patients

(authors own experience and peer consensus), the underlying mechanism and efficacy is not yet fully understood.

Low total body magnesium results from the direct effect of alcohol on the nephron, which causes urinary Mg2+ wastage. Malnutrition and poor dietary intake of magnesium also contribute to poor levels of total body magnesium.

Clinician's often fail to recognise the presence of magnesium deficiency in their patients as they rely on serum values of magnesium. The measureable serum value reflects only 0.15% of total body magnesium, as magnesium is predominantly intracellular and protein bound. Serum values do not drop until critical deficiency exists. Without correction of baseline magnesium deficiency there may be impaired utilisation of thiamine.

The Cochrane review states that there is insufficient evidence as to the duration of treatment and dosages of Thiamine required for the treatment of Wernicke-Korsakoff Syndrome, while acknowledging that thiamine utilization in patients experiencing alcohol withdrawal is probably influenced by Mg2+ status.

Current evidence consists mainly of case reports and clinical observations. Given the weight of biochemical evidence available it is surprising that this role has not been clarified in a clinical study context. A comprehensive search of the literature revealed only one clinical study (co-written by this author) comparing effects of thiamine alone versus thiamine and magnesium sulphate on Red Cell Transketolase (TKA) in alcoholic patients.  In this study, a more rapid recovery of the thiamine dependent enzyme Red Cell TKA occurred, when 2 grams magnesium sulphate was delivered simultaneously with thiamine than in a similar patient group treated with thiamine alone, however this study was not fully controlled.

The Scottish Intercollegiate Guidelines Network (SIGN) also identify the dosage and duration of Thiamine administration as an area of research to be encouraged. The role of Mg2+ as an essential cofactor has a definite relevance to this question as Mg2+ may be influential in determining efficacy.

In this study we would like to extend out previous work by randomising alcoholic patients to treatment with either thiamine alone, magnesium sulphate alone (with delayed thiamine), or

concurrent administration of thiamine plus magnesium sulphate, to determine whether treatment with magnesium sulphate has any effect on its own on red blood cell transketolase activity, or only acts to increase the effect of thiamine.

# **1.3 Study hypothesis**

Hypothesis: That magnesium administration enhances the biochemical response to thiamine.

# 2. STUDY OBJECTIVES

This is a single-centre, randomised, parallel group study to determine the effects of

- IV thiamine
- IV magnesium sulphate
- IV thiamine plus IV magnesium sulphate

on red blood cell TKA in a cohort of alcoholic patients admitted through A&E.

#### • Primary Objective

To determine whether Magnesium administration enhances the biochemical response to thiamine as measured by the activity of the enzyme transketolase in red blood cells

#### • Secondary Objectives

• To determine effect of the administration of thiamine alone, magnesium sulphate alone, or both together on plasma lactate concentrations, vitamins A, B1, B2, B6, B9 B12, C, D, E and K and trace elements (copper, manganese, copper and zinc)

# 3. STUDY DESIGN

This is a 3- arm randomised, open label, controlled study in a cohort of alcoholic patients admitted through A&E. Patients will be randomised to concurrent infusion of one of the following:

- Arm 1: IV thiamine
- Arm 2: IV magnesium sulphate followed by delayed IV thiamine
- Arm 3: IV thiamine and IV magnesium sulphate

Thiamine will be administered as IV Pabrinex, a compound preparation which also contains B vitamins and vitamin C. Administration of IV Pabrinex is standard care in this patient group and magnesium sulphate is routinely co-administered at Glasgow Royal Infirmary.

# 3.1 Study Population

A total of 120 patients will be recruited to this study, with 40 being randomised to each arm i.e.

- Arm 1: IV thiamine (Pabrinex)
- Arm 2: IV magnesium sulphate followed by delayed thiamine (Pabrinex)
- Arm 3: IV thiamine (Pabrinex) and IV magnesium sulphate

Patients will be identified by ED staff on presentation to the ED.

# 3.2 Inclusion criteria

- Written informed consent
- Male or non-pregnant or breastfeeding females ≥18 years of age For women of childbearing potential a negative pregnancy test will be required prior to treatment.
   (Women of non-childbearing potential are defined as those defined as women who are post-menopausal or permanently sterilised (e.g. hysterectomy, tubal occlusion, bilateral salpingectomy).
- Chronic alcohol dependence as confirmed by
  - FAST questionnaire
  - GMAWS scale

# 3.3 Exclusion criteria

- Unable to give consent
- Less than 18 years of age
- Chronic renal or hepatic failure/hepatic encephalopathy (investigator assessment as documented in past medical history i.e. Clinical Portal.)
- Known hypersensitivity or previous allergy to any of the active substances in either trial medication, or to excipients
- Severe concurrent medical condition that would prevent participation in study procedures (e.g. myasthenia gravis, clinically significant cardiac disease, or cardiac failure with severe pulmonary oedema)

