Statistical Analysis:	A three group study was designed to detect a minimum biochemically significant difference of 0.16 in the change from baseline between the groups, with 80% power and a 5% significance level. total sample size = 120. Methodology: One way ANOVA	

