## 3.5 Assessment and management of risk

As above, there are three arms to this study. Our previous study examined the effect of thiamine and magnesium, as compared to thiamine alone, on TKA activity. This demonstrated a significant increase in TKA activity in the magnesium and thiamine group as compared to the thiamine group. It is therefore necessary to include the magnesium sulphate arm to this study to confirm this effect was not directly attributable to Magnesium separately, and to elucidate the degree of synergism that may exist between magnesium and thiamine.

Alcoholism is a disease of malnutrition. Dietary deficiencies develop over weeks, months and years. We appreciate that the two hour delay to Pabrinex administration, represents a delay to standard treatment in the Magnesium group (with delayed Pabrinex). However there is no evidence in the literature to indicate that a real time delay of two hours may disadvantage a patient, or that a single treatment of Pabrinex can reverse the chronic changes associated with Vitamin B1 (Thiamine) deficiency. It is our view therefore that a two hour delay will not disadvantage the patients randomised to this group. Indeed a 2 hour delay is not uncommon in the Emergency Department (ED) for any treatment due to the acuity and volume of patients attending a busy inner city ED. All patients attending the ED should be treated and discharged within the 4 hour window, as dictated by the national access target for emergency care.

Patients will be identified at triage in order to ensure adequate time to recruit, consent and obtain repeat samples at the 2 hour time interval post administration of treatment whilst still meeting national targets. Eligible patients may therefore be seen earlier in their patient journey which may offset potential delays due to study involvement. The net effect will be that patients randomised to the Magnesium group, will therefore receive their Pabrinex at approximately the same point in their patient journey, as if the study were not ongoing.

Magnesium sulphate and pabrinex are routinely administered to this patient group in the ED at GRI.

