## 4.2 Randomisation

Randomisation will be performed in advance by the study statistician and opaque envelopes detailing the subject number and treatment allocation prepared. Patients will be sequentially assigned a subject number once eligibility is confirmed and the corresponding treatment assignment envelope opened. The opened enveloped will be retained and attached to the patient's case report form (CRF)

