#### Power and Sample Size

Choosing the higher st dev to be more conservative, a three group study was designed to detect a minimum biochemically significant difference of 0.16 in the change from baseline between the groups, with 80% power and a 5% significance level. This requires 37 participants to be randomised to each arm of the study. We therefore propose a total sample of 120 to account for any drop-outs or missing data.

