# **APPENDIX A:**

# Patient details : CHI / age

P/C: alcohol withdrawal, seizure, fall, recurrent falls , head injury, sepsis

PM/SH:

Have you been prescribed thiamine?

Do you regularly take thiamine or multi-vitamin tablets?

Medications: Antacid stomach medication PPi/H2 antagonist , Loop diuretics, Digoxin

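### The eligibility and randomisation rules do not keep out a patient already randomised, or one given IV Pabrinex or IV magnesium earlier in the same attendance

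*Combined protocol and SAP*

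**What the plan says.** Arm numbers here follow section 3: Arm 1 thiamine, Arm 2 magnesium with delayed thiamine, Arm 3 both. The synopsis numbers the last two the other way round.

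**Who may enter.** Section 3.2 asks for consent, adult age, a pregnancy and breastfeeding condition, and alcohol dependence on FAST or GMAWS. Section 3.3 lists five exclusions: inability to consent, age under 18, chronic renal or hepatic failure, allergy, and severe concurrent illness. The allergy item, "Known hypersensitivity or previous allergy to any of the active substances in either trial medication, or to excipients", is the only one that refers to the study drugs. None concerns earlier receipt of either drug or earlier participation.

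**How they enter.** Section 4.2 says "Patients will be sequentially assigned a subject number once eligibility is confirmed", after which the matching envelope is opened. It describes no check for a previous entry.

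**Site practice.** Section 3.5 says "Magnesium sulphate and pabrinex are routinely administered to this patient group in the ED at GRI", section 3 says "magnesium sulphate is routinely co-administered at Glasgow Royal Infirmary", and section 6.3.2 calls Pabrinex on admission standard care. Sections 6.2 and 6.4.2 leave magnesium to the physician's discretion, and the synopsis says that co-supplementation is not routine.

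**Text that bears on the gap.** Patients are identified on presentation (4.1) and at triage (3.5). All procedures take place in a single visit (4.3), and each drug is given to a participant only once (6.3.1, 6.4.1). Baseline and 2-hour samples include TKA, thiamine and magnesium (4.3). Appendix A asks about prescribed thiamine and "Do you regularly take thiamine or multi-vitamin tablets". It does not ask about earlier IV Pabrinex or magnesium, and no eligibility or analysis text uses the answers.

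**Analysis.** The synopsis gives "Methodology: One way ANOVA". Section 8 sizes the trial for "a minimum biochemically significant difference of 0.16 in the change from baseline between the groups, with 80% power and a 5% significance level".

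**The concern.** The trial asks whether magnesium enhances the TKA response to thiamine. By the protocol's own rationale (1.2), the reason to expect this is that uncorrected magnesium deficiency impairs thiamine use. Three kinds of entry could spoil that comparison, and nothing written prevents them:

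- A patient given magnesium before the baseline sample and then allocated to Arm 1 has in effect received both drugs, so Arm 1 moves towards Arm 3.
- A patient given Pabrinex before the baseline sample and then allocated to Arm 2 is not a test of magnesium alone. Section 3.5 says that Arm 2 exists to show whether the earlier effect was due to magnesium by itself.
- A patient randomised at an earlier attendance and entered again supplies a second record that is not independent of the first. One-way ANOVA assumes independent records.

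The first two can cost power and blur interpretation. The third means fewer than 120 independent patients behind a nominal 120.

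**Working it through.** **1. Inputs**

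- Difference 0.16, power 80%, significance level 5% (sections 8.1 and 8.2).
- SD 0.2176, the larger of the two pilot SDs (0.2176 and 0.1214, section 8.2). The plan's reason is "Choosing the higher st dev to be more conservative".
- One-way ANOVA, three groups (synopsis).
- 37 per arm required and 120 in total (section 8), that is 40 per arm (3.1).
- Share f of patients who contribute no contrast: not in the documents. I assume 0 to 20%.

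**2. Reproduce the plan's figure**

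Put the three means at −0.08, 0 and +0.08, so that the extremes differ by 0.16 with the third midway (the least favourable case). The noncentrality parameter is

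λ = n × [2 × (0.16/2)²] / SD² = n × 0.0128 / 0.04735 = 0.2703 n.

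At n = 37, λ = 10.00 and the noncentral F distribution gives 80.4% power. At n = 36 it gives 79.2%. The stated 37 per arm is therefore right. 37 × 3 = 111, and 1 − 111/120 = 7.5% is the implied allowance for drop-out. If all 40 per arm are evaluable, λ = 10.81 and power is 83.6%.

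**3. Effect of non-contributing patients**

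If a share f in each arm contributes no contrast and the SD stays at 0.2176, the difference becomes 0.16 × (1 − f) and λ is multiplied by (1 − f)².

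| f | Patients of 120 | Difference | λ, 37/arm | Power, 37/arm | λ, 40/arm | Power, 40/arm | n per arm for 80% |
|---|---|---|---|---|---|---|---|
| 0 | 0 | 0.160 | 10.00 | 80.4% | 10.81 | 83.6% | 37 |
| 5% | 6 | 0.152 | 9.03 | 76.0% | 9.76 | 79.5% | 41 |
| 10% | 12 | 0.144 | 8.10 | 71.1% | 8.76 | 74.7% | 46 |
| 20% | 24 | 0.128 | 6.40 | 60.1% | 6.92 | 63.8% | 57 |

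Even with no drop-out at all, power falls just below 80% at f = 5%, which is 2 patients per arm.

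**4. Keep or exclude**

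Patients excluded before randomisation are replaced by later recruits, so power stays at 83.6% with 40 evaluable per arm. If they could not be replaced, 40 × (1 − f) per arm would remain (38, 36 and 32) at the full difference of 0.16. Power would then be 81.5%, 79.2% and 73.9% for f = 5%, 10% and 20%. Under the same assumption, keeping such patients gives 79.5%, 74.7% and 63.8%.

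**5. Repeat entry**

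This calculation does not cover non-independence. The number of repeat entries cannot be derived from the documents, and I put no figure on it.

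**The case against.** The case for the plan is substantial.

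- **Same-attendance dosing is unlikely.** Patients are found at triage, and baseline bloods come before the study infusions. This stands as mitigation. It does not stop a non-study dose given before the baseline sample.
- **Re-entry sits badly with the text.** Single-visit procedures, one treatment with each drug and a count of 120 patients all suggest one entry per person. But these describe conduct within the study, and section 6.3.1 leaves further Pabrinex to standard care. None is an eligibility rule. Equally, the plan nowhere says that a returning patient should receive a second number; it is silent.
- **Randomisation balances earlier exposure in expectation.** This is right. A reader might infer bias between the arms, and the documents do not support that. The possible harm is to power and interpretation.
- **The mechanism is not quantified.** No duration of carry-over is given for either infusion. A patient who had thiamine alone earlier might still respond to magnesium, so setting the contrast to zero is a worst case. The pilot's eligibility is not described, so its SD may already reflect some pre-treated patients.
- **Site practice is described inconsistently.** The statements on magnesium conflict and need to be reconciled. The point does not depend on how, because even discretionary use leaves the gap, and Pabrinex as standard care is not in dispute.
- **Baseline TKA, thiamine and magnesium are measured.** Recent repletion might therefore be visible. What stands is that no planned analysis uses these values.

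A reader might also infer that recent treatment at earlier attendances calls for a fixed washout. The documents cannot support the length of such a window, and it would cost recruitment in a single-centre, 12-month study without external funding for a gain that cannot be quantified.

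**Conclusion.** The gap is real and limited. Sections 3.2, 3.3 and 4.2 do not bar a patient already randomised, or one given either study drug intravenously earlier in the same attendance before the baseline sample. Such patients could dilute the Arm 3 versus Arm 1 contrast, blur Arm 2 and break independence. The documents do not show that this will happen, or how often.

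The power figures are conditional. They assume complete loss of contrast in a share f, the same f in each arm, an unchanged SD of 0.2176, and a third mean midway between the extremes. On those terms, f = 5%, 10% and 20% gives 79.5%, 74.7% and 63.8% with 40 evaluable per arm, and 76.0%, 71.1% and 60.1% with 37. The sample size arithmetic itself is correct; it simply leaves little slack.

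A reader might prefer the pairwise two-sided t-test of Arm 3 against Arm 1, for which power at 37 per arm is 87.7%, 80.2% and 70.4% at f = 0, 10% and 20%. Those figures are arithmetically right, but they do not describe the planned ANOVA.

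**What to change.** 1. Add two exclusions to section 3.3: (a) previous randomisation in this study; (b) IV Pabrinex or IV magnesium sulphate already given in this attendance before the baseline sample. Have both checked when eligibility is confirmed, before a number is assigned under 4.2.
2. Do not add a fixed look-back exclusion for earlier attendances. Record earlier IV Pabrinex and magnesium from Clinical Portal, which section 3.3 already names as a source, together with the Appendix A answers on thiamine and vitamins. Pre-specify a sensitivity analysis by recorded exposure.
3. Pre-specify adjustment for baseline TKA, which is already measured.
4. Reconcile the statements on magnesium use in the synopsis and sections 3, 3.5, 6.2 and 6.4.2.

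The cost is a short amendment, a brief record check and slightly slower recruitment. The exclusions decide only who enters the trial; care outside it is unchanged. The CRF is not among the documents, so some of the recording may already be in place.

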# 3.4 Withdrawal of subjects

Participants have the right to withdraw from the trial at any point for any reason. Data collected up to the point of withdrawal will be retained. The investigator can also withdraw patients from the study intervention in the event of inter-current illness, protocol violations or any other relevant reasons.

## 3.5 Assessment and management of risk

As above, there are three arms to this study. Our previous study examined the effect of thiamine and magnesium, as compared to thiamine alone, on TKA activity. This demonstrated a significant increase in TKA activity in the magnesium and thiamine group as compared to the thiamine group. It is therefore necessary to include the magnesium sulphate arm to this study to confirm this effect was not directly attributable to Magnesium separately, and to elucidate the degree of synergism that may exist between magnesium and thiamine.

Alcoholism is a disease of malnutrition. Dietary deficiencies develop over weeks, months and years. We appreciate that the two hour delay to Pabrinex administration, represents a delay to standard treatment in the Magnesium group (with delayed Pabrinex). However there is no evidence in the literature to indicate that a real time delay of two hours may disadvantage a patient, or that a single treatment of Pabrinex can reverse the chronic changes associated with Vitamin B1 (Thiamine) deficiency. It is our view therefore that a two hour delay will not disadvantage the patients randomised to this group. Indeed a 2 hour delay is not uncommon in the Emergency Department (ED) for any treatment due to the acuity and volume of patients attending a busy inner city ED. All patients attending the ED should be treated and discharged within the 4 hour window, as dictated by the national access target for emergency care.

Patients will be identified at triage in order to ensure adequate time to recruit, consent and obtain repeat samples at the 2 hour time interval post administration of treatment whilst still meeting national targets. Eligible patients may therefore be seen earlier in their patient journey which may offset potential delays due to study involvement. The net effect will be that patients randomised to the Magnesium group, will therefore receive their Pabrinex at approximately the same point in their patient journey, as if the study were not ongoing.

Magnesium sulphate and pabrinex are routinely administered to this patient group in the ED at GRI.

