# 8. STATISTICS AND DATA ANALYSIS-

#### 8.1 Power and Sample Size

Choosing the higher standard deviation to be more conservative, a three group study was designed to detect a minimum biochemically significant difference of 0.16 in the change from

baseline between the groups, with 80% power and a 5% significance level. This requires 37 participants to be randomised to each arm of the study. We therefore propose a total sample of 120 to account for any drop-outs or missing data.

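### The magnesium-only arm is there to separate magnesium's own effect from synergism with thiamine, but the one-way ANOVA, the only analysis named, estimates neither

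*Combined protocol and SAP*

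**What the plan says.** Section 3.5 gives the magnesium-only arm (magnesium sulphate, with Pabrinex after the second blood sample) two purposes: "to confirm this effect was not directly attributable to Magnesium separately", and "to elucidate the degree of synergism that may exist between magnesium and thiamine". Section 1.2 puts the first as an open question, whether magnesium "has any effect on its own on red blood cell transketolase activity, or only acts to increase the effect of thiamine". The rationale in the synopsis asks the same.

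The only analysis named is in the synopsis: "Methodology: One way ANOVA". Section 8.2 is headed as the statistical analysis plan but holds only the pilot summary and a repeat of the sample-size paragraph. Section 8.1 sizes the trial "to detect a minimum biochemically significant difference of 0.16" between groups in the change from baseline, "with 80% power and a 5% significance level". Section 4.4.1 lists the pre-to-post change in TKA under each regimen, magnesium included, as the primary outcome. No within-arm estimate, pairwise procedure or additivity contrast is given, and there is no untreated arm.

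**The concern.** Write T and M for the changes due to thiamine and magnesium alone, and S for synergism. With no change in untreated patients, the arm means are T, M and T + M + S. Then:

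- combined minus thiamine = M + S
- combined minus magnesium = T + S

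Neither difference separates M from S. A positive combined-minus-thiamine difference may be all M (magnesium simply adds its own effect) or all S (magnesium enhances the response to thiamine). The primary objective concerns enhancement, and section 3.5 calls the third arm necessary in order to tell these apart. An ANOVA of equal means leaves the question open, so the rule for answering it would be chosen after open-label data have been seen.

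**Working it through.** **Inputs.** Pilot table in 8.2: combined mean 0.3211, SD 0.2176 (n = 18); thiamine mean 0.1433, SD 0.1214 (n = 12). Section 8.1: difference 0.16, the higher SD, 80% power, 5% level, 37 per arm. Section 3.1: 40 per arm. The documents give no mean or SD for magnesium alone. The values of M below are assumptions, with SD 0.2176 in every arm and no untreated change.

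**1. The plan's own figure.** Take an omnibus F test with three arms, largest difference 0.16 and the third mean midway. The noncentrality is n × Σ(μᵢ − μ̄)² / SD² = 37 × (2 × 0.08²) / 0.2176² = 10.0, giving power 80.4% (83.6% at 40 per arm). The stated 37 per arm reproduces and is not in dispute.

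**2. Does combined above both single drugs separate the explanations?** Simulated normal data, 100,000 trials per scenario. The unadjusted columns require a significant F and both pairwise tests significant at 5%.

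| Scenario | Means T / M / combined | 37 per arm, unadjusted | 40 per arm, unadjusted | 40 per arm, Tukey |
|---|---|---|---|---|
| Pure addition (S = 0) | 0.1433 / 0.16 / 0.3033 | 74% | 78% | 64% |
| Magnesium inert (S = 0.16) | 0.1433 / 0 / 0.3033 | 88% | 90% | 82% |

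Check on the second row: combined is nearly always above magnesium, so the rate is the power for combined against thiamine. At 40 per arm, 0.16 / (0.2176 × √(2/40)) = 3.29, and Φ(3.29 − 1.98) ≈ 0.90.

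The pattern is common under both explanations. The pure-addition rate depends on thiamine's own effect: with T = 0.10 and M = 0.16 it is about 51% (40 per arm, unadjusted).

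**3. Magnesium's own change.** SE = 0.2176 / √40 = 0.0344. The 95% CI half-width is 2.02 × 0.0344 = 0.070 (0.073 at 37). A true change of 0.16 is detected in about 99.5% of trials. A true 0.08 is non-significant in 38% (41% at 37), so non-significance is weak evidence of no effect.

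**4. Synergism.** Combined minus thiamine minus magnesium = S. Its SE is SD × √(3/n).

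- 40 per arm: 0.2176 × √(3/40) = 0.0596; half-width 1.98 × 0.0596 = 0.118. Power for S = 0.16: 0.16 / 0.0596 = 2.68; Φ(2.68 − 1.98) ≈ 76%.
- 37 per arm: SE 0.0620, half-width 0.123, power about 73%.
- Under pure addition it is significant in 5% of trials (two-sided).
- 80% power for 0.16 needs about 3 × (0.2176 × 2.80 / 0.16)² ≈ 44 per arm.

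**5. Using 0.16 as a clearance limit.** Suppose magnesium were cleared whenever the upper 95% limit of its own change is below 0.16. A true own effect of 0.08 lies 0.08 below the limit, or 0.08 / 0.0344 = 2.33 SE, so it is cleared with probability about Φ(2.33 − 2.02) ≈ 62% at 40 per arm. In about 25% of trials it would be cleared although the CI also excludes zero.

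**6. Untreated drift.** If TKA moves by d in everyone, the magnesium-only mean estimates M + d and the contrast estimates S − d.

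**The case against.** A reader might infer that the plan intends to take combined above each drug alone as confirmation, or that the ANOVA itself usually yields that pattern. The documents do not support either. No passage states such a rule, the omnibus F test does not show which arms differ, and no pairwise procedure is planned. The 78% describes a plausible follow-up, not a planned one, and it depends on a thiamine mean estimated from 12 pilot patients.

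Nor do the documents set out throughout to prove a negative. Only the clause in 3.5 is worded that way; 1.2 and the synopsis ask an open question.

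It is also fair to say that 4.4.1 already makes the magnesium arm's own change a primary outcome. In the pure-addition scenario with M = 0.16, its CI would almost always exclude zero, so an investigator who looked would probably not be misled.

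These points limit the claim without removing it. The data will exist, but no inference is attached to them. For smaller own effects, such as 0.08, looking at significance alone would often mislead.

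**Conclusion.** The concern holds as a mismatch between the stated purpose of the third arm and the only analysis named. The algebra does not depend on any percentage. The simulated rates (about 78% against 90% at 40 per arm) illustrate how poorly pairwise results would discriminate. They rest on the pilot thiamine mean, a common SD of 0.2176, normal data, an assumed M and no untreated change.

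The sample size is adequate for its stated F test, gives a usable CI for magnesium's own change, and is slightly short of 80% power for a synergism contrast of 0.16.

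It is tempting to treat the "minimum biochemically significant difference of 0.16" as a ready-made margin for declaring that magnesium has no effect of its own. The documents set it as a between-group difference to detect, not as a negligible effect. It exceeds thiamine's whole pilot change (0.1433) and is 0.16 / 0.1778 = 90% of the pilot gain (0.3211 − 0.1433 = 0.1778).

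**What to change.** Add to the statistical entry in the synopsis and to 8.2, on the same change-from-baseline scale as the 0.16 (4.4.1 speaks of relative change, and additivity depends on the scale, so it must be fixed first):

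- The mean TKA change in the magnesium-only arm is estimated with a two-sided 95% CI, reported as the range of own effects not excluded.
- Synergism is estimated by combined minus thiamine minus magnesium, with a two-sided 95% CI.
- Neither a non-significant change in the magnesium-only arm nor a result of combined above magnesium alone counts as evidence that magnesium has no effect of its own.
- Both estimates assume no change in TKA without treatment over the sampling interval, because there is no untreated arm.

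Do not adopt an upper limit below 0.16 as the rule for concluding that the effect is not magnesium's own.

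The cost is a few sentences of text, with no extra patients, samples or assays. The downsides are that power for a synergism of 0.16 is 73% to 76% at 37 to 40 per arm, and that an intermediate own effect may have to be reported as unresolved.
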